3.2 Research methods

Through the establishment of a national multi-center cognition and aging cohort, this study will collect relevant demographic information and clinical data, biofluid samples, neuropsychological evaluation, imaging examination, blood examination and other comprehensive evaluation of study subjects, so as to study the epidemiology, influence factors, genetics and pathogenesis, diagnostic standards, prevention and control strategies of dementia and its subtypes. The study flow chart is as follows (figure 1):

3.2.1 Inclusion and exclusion criteria:

Community population: age ≥ 55 years, male or female, with consent to participant the study.

Hospital population: subjects are all over 18 years old. Through clinical evaluation, neuropsychological test, imaging examination, blood and cerebrospinal fluid examination, etc, we will comprehensively evaluate the cognitive function and various test measures.

(1) MCI and its subtypes

Inclusion criteria:

- 1) Diagnosis according to 2004 Peterson's MCI criteria.
- 2) CDR = 0.5.
- 3) Memory loss is prominent, and may also be with other cognitive domain dysfunction.
- 4) Insidious onset, slow progress.
- 5) Not reaching the level of dementia.

Exclusion criteria:

- 1) With history of stroke and a neurological focal sign, the imaging findings are consistent with cerebral small vessal disease (Fazekas score ≥ 2 points).
- 2) Other neurological diseases that can cause brain dysfunction (such as depression, brain tumor, Parkinson's disease, metabolic encephalopathy, encephalitis, multiple sclerosis, epilepsy, brain trauma, normal intracranial pressure hydrocephalus, etc.).
- 3) Other systemic diseases that can cause cognitive impairment (such as liver, renal and thyroid insufficiency, severe anemia, folic acid or vitamin B12 deficiency, syphilis, HIV infection, alcohol and drug abuse, etc.).
 - 4) Mental and neurodevelopmental retardation.
 - 5) Contraindications to MRI.
 - 6) Suffering from a disease that cannot be combined with cognitive examination.
 - 7) Refuse to draw blood.
 - 8) Refuse to sign the informed consent at baseline

(2) Sporadic Alzheimer's disease (SAD)

Inclusion criteria:

- 1) Dementia is diagnosed according to the criteria described by the Diagnostic and Statistical Manual of Mental Disorders, Fourth Edition, Text Revision (DSM-IV-R). The diagnosis of AD is made using the National Institute of Neurologic and Communicative Disorders and Stroke and the Alzheimer's Disease and Related Disorders Association (NINCDS-ADRDA) or National Institute on Aging and the Alzheimer's Association (NIA-AA) criteria.
 - 2) Subjects and their informed persons can complete relevant and follow- up examinations.
 - 3) Subjects or their authorized legal guardians sign the informed consent.

Exclusion criteria:

- 1) With a family history of dementia.
- 2) Other neurological diseases that can cause brain dysfunction (such as depression, brain tumor, Parkinson's disease, metabolic encephalopathy, encephalitis, multiple sclerosis, epilepsy, brain trauma, normal intracranial pressure hydrocephalus, etc.).
- 3) Other systemic diseases that can cause cognitive impairment (such as liver, renal and thyroid insufficiency, severe anemia, folic acid or vitamin B12 deficiency, syphilis, HIV infection, alcohol and drug abuse, etc.).
 - 4) Mental and neurodevelopmental retardation.
 - 5) Contraindications to MRI.
 - 6) Suffering from a disease that cannot be combined with cognitive examination.
 - 7) Refuse to draw blood.
 - 8) Refuse to sign the informed consent at baseline

(3) Familial Alzheimer's disease (FAD)

Inclusion criteria:

- 1) Written informed consent obtained from participant or legal guardian prior to any study-related procedures.
- 2) Members in FAD pedigree (FAD is defined as at least two first- degree relatives suffer from AD).
- 3) Aged 18 (inclusive) or older.
- 4) At least two persons who can provide reliable information for the study.

Note: Dementia is diagnosed according to the criteria described by DSM-IV-R. The diagnosis of AD is made using NINCDS-ADRDA or NIA-AA criteria. A diagnosis of MCI is assigned according to Petersen criteria.

Exclusion criteria:

1) Dementia caused by other factors such as depression, other psychiatric illnesses, thyroid dysfunction, encephalitis, multiple sclerosis, brain trauma, brain tumor, syphilis, acquired immunodeficiency syndrome (AIDS), Creutzfeldt-Jakob disease and other types of dementias such as vascular dementia (VaD), frontotemporal dementia (FTD), dementia with Lewy bodies (DLB), and Parkinson's

disease dementia (PDD).

- 2) MRI and laboratory tests do not support or rule out a diagnosis of AD.
- 3) Severe circulatory, respiratory, urinary, digestive, hematopoietic diseases (such as unstable angina, uncontrollable asthma, active gastric bleeding) and cancer.
- 4) Participant has severe psychiatric illness or severe dementia that would interfere in completing initial and follow-up clinical assessments.
 - 5) With history of alcohol or drug abuse.
 - 6) Pregnant or lactating women.
 - 7) No reliable insiders.
 - 8) Refuse to sign the informed consent at baseline.

(4) Vascular dementia (VaD)

Inclusion criteria:

Diagnosis for probable VaD according to NINDS-AIREN diagnostic criteria.

MRI inclusion criteria:

All patients who meet clinical inclusion criteria should accept MRI scans which include an assessment of hippocampal volume.

a. multiple (\geq 3) supratentorial subcortical small infarcts (3-20 mm in diameter) with or without any degree of white matter lesion (WML); or moderate to severe WML (Fazekas score \geq 2), with or without small infarction; or \geq 1 subcortical small infarct in key regions, such as caudate nucleus, globus pallidus, or thalamus.

b. no cortical and watershed infarction, hemorrhage, hydrocephalus, or WML with specific causes (such as multiple sclerosis).

c. no hippocampus or entorhinal cortex atrophy (MTA score = 0 point).

Exclusion criteria:

- 1) Other neurological diseases that can cause brain dysfunction (such as depression, brain tumor, Parkinson's disease, metabolic encephalopathy, encephalitis, multiple sclerosis, epilepsy, brain trauma, normal intracranial pressure hydrocephalus, etc.).
- 2) Other systemic diseases that can cause cognitive impairment (such as liver insufficiency, renal insufficiency, thyroid insufficiency, severe anemia, folic acid or vitamin B12 deficiency, syphilis, HIV infection, alcohol and drug abuse, etc.).
 - 3) With a history of mental illness or those with congenital mental retardation.
 - 4) Suffering from a disease that cannot be combined with a cognitive examination.
 - 5) Contraindications to MRI.
 - 6) Refuse to draw blood.
 - 7) Refuse to sign informed consent.

(5) Normal control

Inclusion criteria:

- 1) Aged 18 (inclusive) or above.
- 2) Normal MMSE and MoCA evaluations. MMSE>19 points for illiteracy, >24 points for those educated less than 7 years, >27 points for those educated equal to or more than 7 years. MoCA>13 points for illiteracy, >19 points for those educated less than 7 years, >24 points for those educated equal to or more than 7 years.

Exclusion criteria:

- 1) Subjects with abnormal MMSE or MoCA scores.
- 2) Subjects with a history of cerebral infarction, traumatic brain injury or related manifestations in MRI.
- 3) Other neurological diseases that can cause brain dysfunction (such as depression, brain tumor, Parkinson's disease, metabolic encephalopathy, encephalitis, multiple sclerosis, epilepsy, brain trauma, normal intracranial pressure hydrocephalus, etc.).
- 4) Other systemic diseases that can cause cognitive impairment (such as liver, renal and thyroid insufficiency, severe anemia, folic acid or vitamin B12 deficiency, syphilis, HIV infection, alcohol and drug abuse, etc.).

- 5) Mental and neurodevelopmental retardation.
- 6) Suffering from a disease that cannot be combined with a cognitive examination.
- 7) Contraindications to MRI.
- 8) Refuse to draw blood.
- 9) Refuse to sign the informed consent at baseline.

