3.1 Research content

[figure not shown]
- 1. Through the collection of basic demographic information and clinical data from the multi-center cohort, we will calculate the prevalence and incidence rate of AD, VaD, other dementia (mixed dementia, FTD, DLB, PDD, alcohol dementia, hydrocephalus dementia, post-traumatic dementia, etc.), and update the numbers every 1-2 years.
- 2. To clarify the conversion pattern from normal elderly to MCI and from MCI to dementia. Through the collection and analysis of current medical history, past history, family history, living habits, drug use, physical examination and other information, we will explore the protective and risk factors of dementia and its main subtypes (AD, VaD, Other dementia), including age, gender, education level, rural/urban, marital status, parental dementia history, dietary habbit, blood pressure, drinking, smoking, diabetes, hyperlipidemia, cerebrovascular disease, heart disease, depression, hearing impairment, exercise habits (Tai chi, etc.), dementia specialist influence on patients, occupation, BMI, lifestyle changes, air pollution, head injury, social contact, low-income, and other unknown protective or risk factors. To investigate the role of ApoE gene, especially ApoE in the disease onset and development, and to explore the non-pharmacological interventions For the study purpose we do follow-up every 2 or 3 years.
- 3. By using exome sequencing, GWAS, WGS and other methods, we will search for new mutations of known pathogenic genes (APP, PSEN1, PSEN2) of AD in China, find new pathogenic genes and susceptible genes of dementia and its main subtypes (AD and VaD), and understand their distribution. We will explore the independent and combined effect of susceptibility gene variation on the risk of illness in Chinese AD population, and to obtain the key mutation sites that have a clear relationship with the incidence of AD. We will do regular follow up visits for the FAD members with new mutations of pathogenic genes, and clarify the important role of new mutations of pathogenic genes during the onset and progression of AD.
- 4. We will collect the biofluids (blood, cerebrospinal fluid, urine, etc.) and ¹⁸F-FDG / ¹¹C-PIB PET/MR multimodal imaging data from people with normal cognition, MCI, AD (sporadic and familial) and VaD, and conduct regular follow up. Discover and verify the

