4.2.11 Clinical Dementia Rating Scale (CDR) (83)

The CDR is a refinement of information that the doctor obtains through conversations with the patient and his/her family, and to assess the degree of impairment of the patient's cognitive function, and then to quickly assess the severity of the patient's condition. The assessment of cognitive domains consists of six items: memory, orientation, judgment and problem solving, work and social ability, family life and hobbies, and independent living ability. The judgment is in five levels, "normal CDR=0, suspected dementia CDR=0.5, mild dementia CDR=1, moderate dementia CDR=2, severe dementia CDR = 3". The CDR-SOB (CDR sum of box) total score is a simple sum of the scores of the six items. CDR sum of boxes adds up the 6 items, and the total score ranges from 0 to 18. As long as the score is greater than 0, the subject has at least one cognitive impairment. Generally, the change value of CDR sum of boxes can be used in clinical trials to obtain more accurate cognitive evaluation (117). CDR is a widely used measure of the severity of dementia.

5. Imaging examination

At each assessment, subjects will receive MRI, PET, and carotid ultrasound. PET imaging includes FDG-PET and amyloid PET scans.

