5.1 Imaging equipment and qualifications

Xuanwu Hospital and each sub-center have advanced imaging equipment. Most centers have Siemens or GE full-body MRI scanner, and some centers have PET/MR integrated whole body scanner or PET scanner. Each center has the license for the use of radioactive drugs by the National Food and Drug Administration (fourth category) and has the qualification to prepare new drugs (tracers) for research and development.

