5.2 MRI

MRI should be performed within 1 month before or after neuropsychological testing (with no new vascular disease events). All subjects should be checked for MRI contraindications before MRI scanning, such as the presence of metal implants in vivo. Remove active metal objects from the body before examination. After the subjects lie down, his right temple is used as a stereotactic marker, and the scan follows given directions. Three dimensional T1 weighted images of the whole brain were obtained. All subjects will undergo regular scan (T1WI, T2WI, FLAIR, DWI, MRA) and hippocampal phase scan (coronal T1-FLAIR sequence). Image acquisition is completed by radiology department of each center, stored and transmitted in DICOM format, and then image processing is carried out to obtain brain volume, cortex thickness and other indicators. Fazekas score and MTA score were obtained and used as location and quantitative indicators of white matter lesions and gray matter atrophy.

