6.2.2 Cerebrospinal fluid sample

Lumbar puncture should be done in the morning. To eliminate the impact of puncture bleeding on the quality of cerebrospinal fluid specimens, the first 1-2 ml of CSF should be discarded. 10ml CSF for biomarker analysis should be collected. Centrifuge within 2 hours after collection (2000 rpm for 10 minutes), then pipette and distribute the supernatant into ten of 1.5ml centrifugal tubes, 1 ml per tube. Centrifugal tubes are immediately stored at a -80°C fridge.

7. Informed consent

In this study, a series of memory and intelligence tests will be performed on participants, and if necessary, auxiliary examination will be arranged to confirm the diagnosis. After that, regular follow-up will be arranged for each person to tract the change of disease status. Participants and their families should be informed that they should sign an informed consent form after fully understanding the research, and should be reminded that participation in the study is voluntary.

According to the current edition of the Declaration of Helsinki, the principle of informed consent will be implemented before protocol procedures are carried out. Information about the research content should be provided in both oral and written form and reviewed by an ethics committee. Subjects, relatives and guardians must have ample opportunity to inquire about details of the study. The informed consent should be in the language and script that subjects or legal representative can fully understand. During the clinical study, subjects can keep abreast of their research information.

Informed consent will be recorded by using a written document approved by the Ethics Committee and signed by the subject and/or legally authorized representative. The written informed consent document will embody the elements of informed consent as stated in the Helsinki Declaration and will comply with local regulations. Informed consent should mainly include the following contents:

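### The protocol requires no pregnancy or lactation check before radiotracer PET in any group, and normal controls from age 18 have no such exclusion at entry

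*Protocol*

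**What the plan says.** Section 3.2.1 gives separate entry lists for the five hospital groups. Exclusion 6 for FAD reads "Pregnant or lactating women". The lists for MCI, sporadic AD, vascular dementia and normal control have no such item. The age criterion for normal controls is "Aged 18 (inclusive) or above", the same floor as for FAD.

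On who is imaged, section 3.1 item 4 plans "multimodal imaging data from people with normal cognition, MCI, AD (sporadic and familial) and VaD, and conduct regular follow up", and names the FDG and 11C-PIB tracers. The opening of section 5 says: "At each assessment, subjects will receive MRI, PET, and carotid ultrasound". It adds: "PET imaging includes FDG-PET and amyloid PET scans". Table 1 in section 3.2.2 marks imaging at both baseline and follow-up.

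Two places limit this. Section 5.1 says that "some centers have PET/MR integrated whole body scanner or PET scanner", so not every center can do PET. Section 7 says that "if necessary, auxiliary examination will be arranged to confirm the diagnosis".

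On checks before scanning, section 5.2 states: "All subjects should be checked for MRI contraindications before MRI scanning". Section 5.3.1 sets a one-month window, a six-hour fast and a glucose limit for FDG-PET. Section 5.3.2 sets no condition before 11C-PIB PET. Section 8.4 acknowledges radiation exposure and does not mention pregnancy.

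**The concern.** PET with FDG or 11C-PIB exposes the participant to radiation, and in a cohort study the scan is done for research. A plan that writes down a contraindication check for MRI, and fasting and glucose for FDG-PET, would be expected to write down a pregnancy and lactation check for the radiotracer scans too. It does not. The one related rule is an entry criterion for a single group.

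Normal controls and FAD members are the groups most likely to include women of childbearing age, and only FAD has the exclusion. The FAD exclusion acts mainly at entry, while imaging is repeated at follow-up. Section 5.3 would therefore not pick up a pregnancy arising between visits, even in an FAD member.

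The stake is avoidable exposure of a fetus or infant. No estimate and no stated aim of the study is affected.

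**Working it through.** The protocol gives no figure to reproduce. The check is a reading of the entry lists, the imaging sections and the general safety clauses.

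**Step 1. Entry lists (section 3.2.1).**

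| Hospital group | Exclusions listed | Pregnancy or lactation items |
|---|---|---|
| MCI | 8 | 0 |
| Sporadic AD | 8 | 0 |
| FAD | 8 | 1 (no. 6) |
| Vascular dementia | 7 | 0 |
| Normal control | 9 | 0 |

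One group in five has the item. The community cohort enters at age 55 or over and is essentially unaffected. The control list does exclude MRI contraindications, but section 5.2 illustrates these with metal implants. That item does not address tracer radiation or lactation.

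**Step 2. Are controls meant to have PET?** Yes, at least some. Section 3.1 item 4 includes people with normal cognition, and section 5 places both tracers at each assessment. Section 3.2.2 (1) restricts baseline testing of controls to MMSE and MoCA, but that concerns the cognitive part and not imaging.

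**Step 3. Scans per assessment for one control.**
- Minimum: 0, where the center has no PET (section 5.1) or the examination is not arranged (section 7).
- Maximum: 1 FDG + 1 11C-PIB = 2.

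**Step 4. Checks before each type of scan.**

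| Scan | Condition stated | Pregnancy or lactation |
|---|---|---|
| MRI (5.2) | contraindication check, one-month window | not named |
| FDG-PET (5.3.1) | one-month window, fast, glucose limit | not named |
| 11C-PIB PET (5.3.2) | none | not named |

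The laboratory items in section 6.1.3 name no pregnancy test.

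**Step 5. Do the general clauses fill the gap?**
- Section 9.1.3 has the quality control committee enforce the entry criteria. For a control there is no pregnancy criterion to enforce.
- Section 3.2.2 (5) lets a subject withdraw if safety risks arise, and section 7.3 lets the clinician stop for a health risk. Both depend on the risk having been recognised.
- Section 7.1.2, which prescribes consent content, says that no physical harm will result and mentions neither radiation nor pregnancy.

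None of these requires status to be established before tracer injection.

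**Step 6. How many women?** This needs the number of female controls of childbearing age, the share scanned, and the tracer doses. The protocol gives none of them, so the number and the dose cannot be computed.

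**The case against.** The strongest reply is that this is an unwritten operational step and not an error. Nothing is misstated, and no two sections conflict. Several things outside section 5.3 could catch a pregnancy:
- current history, past history and physical examination at baseline and follow-up (Table 1, sections 4.1.2 and 4.1.6);
- the radioactive-drug licence held by each center (5.1);
- the standard operating procedures of the quality control committee (section 10);
- the researcher's manual used in training (10.2);
- the consent form, which is not in the text available;
- local ethics review and nuclear-medicine practice.

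Most of this stands. A reader might infer that controls are scanned without anyone asking about pregnancy. The protocol supports only that no section shown requires the question. A reader might also infer that every control receives two tracers at each visit. Sections 5.1 and 7 do not allow that, and two is an upper bound.

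A further tempting inference is that a radiation rule was written for FAD and dropped for controls. The protocol gives no reason for the FAD criterion and does not tie it to PET. The FAD list also differs in other ways: it adds severe organ disease, cancer and the lack of a reliable informant, and it has no MRI-contraindication or blood-refusal item. FAD follow-up runs to a separate protocol standard. The contrast shows where the entry gap lies but not how it arose. Nor is the gap in 5.3 confined to controls.

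What the reply does not remove is that the written entry list, followed as it stands, admits a pregnant or lactating control to radiotracer PET. Eligibility and imaging safety belong in the protocol, and this one already writes down its other checks before scanning.

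**Conclusion.** The point holds as a cheap improvement to participant safety. No section shown requires pregnancy or lactation status to be established before FDG or 11C-PIB PET in any group, and the only related rule is the FAD entry exclusion. Normal controls, who also enter from 18 and are among those to be imaged, are eligible for PET while pregnant or lactating.

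The exposure is 0 to 2 radiotracer scans per assessment for an affected participant. The number of such participants is unknown and probably small; that judgement is an assumption, because the protocol does not give the age and sex mix of controls. The conclusion rests on the text available. An explicit check in the unseen operating procedures, manual or consent form would reduce the practical risk but would not change what sections 3.2.1 and 5.3 say.

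**What to change.** Add one sentence to section 5.3, covering both tracers: before each PET session, at baseline and at follow-up, confirm pregnancy and lactation status for women of childbearing potential in every group; if positive, omit or defer PET and still collect the cognitive, blood and other data from a participant who remains eligible.

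Optionally, also add pregnancy and lactation to the normal-control exclusions in section 3.2.1 (5). Alone this is the weaker measure, because it acts mainly at entry and does little for follow-up scans.

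The cost of the first change is one line and a few deferred or missing PET scans. The cost of the second is one line and a few young female controls not enrolled.

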3.2.2 Subject interview

(1) Baseline and follow-up interview items

During the follow-up of the subjects, the research supervisors were responsible for uploading data. Based on population, subjects were divided into community population and hospital population. Hospital population was further divided into MCI, FAD, SAD, VaD, normal control subjects. The supervisors of the centers monitored follow-up visits at different follow-up intervals in different population. The contents of the survey are shown in **Table 1**.

Among them, the community population and normal control cohort only completed MMSE and MoCA for the baseline cognitive assessment part. If the MMSE and MoCA scores did not meet the normal population criteria at the time of follow-up visit, the subject should complete all the assessment scales. The investigator should judge whether the subject meets the criteria for inclusion in other groups in the cohort based on the assessment scores.

Table 1. List of items during baseline and follow-up

Items	Baseline	Follow-up
Informed consent	~	
Personal information	~	V
Current medical history	~	V
habits and customs	~	
Family history	~	
Past history	~	✓
Medication for cognitive impairment	~	✓
Physical examination	~	V
Hachinski ischemic score	~	V
Cognitive assessment	~	V
Mental behavior assessment	~	V
Daily and overall functional assessment	~	V
Image examination	~	V
Laboratory examination	~	✓
Clinical diagnoses	~	V

(2) Follow-up period

The follow-up period was 1-3 years, with an average of 1 year, depending on the subject. Among them, the follow-up period of FAD patients was performed according to the CFAN study protocol standard.

(3) Telephone follow-up

Subjects who were unable to face-to-face follow-up due to geographic reason or severe disease were evaluated by telephone follow-up. The main purpose of telephone follow-up is to keep in touch with the subject, to grasp the subject's changes in cognitive function, learning ability, activities of daily living, social ability, and to collect information on adverse reactions (116).

(4) Consistency of the examination time

All subjects were required to complete all examinations within a 4-week time window, including personal information, clinical assessment, neuropsychological scale testing, biomarker collection, and imaging examination.

(5) Study termination

The main reasons for termination of the study are as follows:

- 1. Violation of the research protocol, no longer meet the inclusion criteria.
- 2. The subject is unwilling or unable to participate.
- 3. Withdraw informed consent.
- 4. The study is terminated by the project leader or the coordination management center.
- 5. Safety risks, subjects may withdraw according to their wishes at any time during the clinical trial if safety risks arise.
- 6. Death.
- 7. Other.

